We propose to build on our established programme of DNA fusion gene vaccination delivered by intramuscular injection and exploiting our unique experience with electroporation, to induce durable immune responses with the aim of controlling disease by precision attack of the tumour by CD8+ T cells. The aim of the trial is to evaluate an identical vaccine strategy in two parallel settings with the purpose of identifying the most promising context for eventual phase III testing. We intend to test the hypothesis that molecular and clinical responses, induced by T cells can be predicted by increases in the number of CD8 T cells, specific for the vaccine-encoded T cell epitopes.

Studying two patient groups will maximise the knowledge gained from this vaccine trial: Patients with CML will allow a direct and objective assessment of the anti-leukaemia effect of vaccination at the molecular level by BCR-ABL and WT1 monitoring.

Patients with AML offer a difficult challenge to haematologists. The advantage of including this patient group is twofold. We can assess the anti-leukaemia effect of vaccination objectively by measuring WT1 gene expression levels. More importantly, we can gain data on the clinically highly relevant question of whether vaccination will prevent relapse in this patient group. Based on the MRC AML 11 trial data, it is anticipated that 60-75% of patients enrolled in this trial will relapse in 2 years (Figure 1) (25).

For both CML and AML the HLA A2 negative patients will be prospectively followed as control groups.

Figure 1. Survival and risk of relapse in AML

Overall survival (A) and relapse risk (B) in MRC AML11 trial are shown by hierarchical risk group. The risk groups were as follows. Favourable group: t(15;17), t(8;21), or inv(16), whether alone or in conjunction with other abnormalities. Intermediate group: normal karyotype, all other noncomplex abnormalities. Adverse group: complex karyotype (5 or more unrelated abnormalities), excluding cases with t(15;17), t(8;21), and inv(16).

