3 TRIAL DESIGN

This is a non-randomised open label, single dose level Phase II study in two patient groups (CML and AML) based on HLA A2 genotype. Consented and eligible HLA A2+ patients will be vaccinated with two DNA vaccines, p.DOM-WT1-37 (epitope sequence: VLDFAPPGA) and p.DOM-WT1-126 (epitope sequence: RMFPNAPYL). Patients with HLA A2-ve genotype will therefore form the unvaccinated control group. The sample size for the HLA A2+ group has been determined using a A'Hern's single stage study design.

Intervention group of HLA A2+ patients:

32 HLA A2 +ve patients with data to at least 16 weeks will be recruited into the CML treatment group.39 HLA A2 +ve patients with data to at least 16 weeks will be recruited into the AML treatment group.

Control groups of HLA A2-negative but otherwise eligible, consenting patients:

CML: Control group: all eligible and consenting patients who are HLA A2 negative AML: Control group: all eligible and consenting patients who are HLA A2 negative

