10 STATISTICS AND DATA ANALYSIS

10.1 SAMPLE SIZE CALCULATION

10.1.1 SAMPLE SIZE CALCULATION FOR CML

The sample size calculation is based on A'Hern's Single-Stage Design and the primary outcome measure of molecular response (BCR-ABL or WT1).

A molecular response (BCR-ABL or WT1) rate of 20% would imply the vaccine clearly warrants further investigation. A molecular response rate of 5% or less would be unacceptable and would indicate the vaccine does not warrant further investigation. The probability of obtaining a false positive result, α (i.e. incorrectly accepting for further study a treatment that has a true PFS rate 30%) is set at 10%. The probability of a false negative result, β (i.e. incorrectly rejecting for further study a treatment with a true PFS rate of 50%) is set at 10%. Using these parameters, $\alpha = 0.1$, $\beta=0.1$, p0=5%, p1=20%, 32 HLA A2+ve patients need to be recruited to the study. The drop-out rate is expected to be less than 10%, hence a total of 36 patients will be recruited.

This trial needs to observe a minimum of 4 out of 32 patients who are molecular responders in order to provide evidence that the vaccine warrants further investigation. Patients will be followed up for 2 years to assess molecular response.

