10.1.2 SAMPLE SIZE CALCULATION FOR AML

The sample size calculation is based on A'Hern's Single-Stage Design and the primary outcome measure of progression free survival (PFS) at 2 years.

A progression free survival rate of 50% at 2 years would imply the vaccine clearly warrants further investigation. A PFS rate of 30% or less at 2 years would be unacceptable and would indicate the vaccine does not warrant further investigation. The probability of obtaining a false positive result, α (i.e. incorrectly accepting for further study a treatment that has a true PFS rate 30%) is set at 10%. The probability of a false negative result, β (i.e. incorrectly rejecting for further study a treatment with a true PFS rate of 50%) is set at 10%. Using these parameters, $\alpha = 0.1$, $\beta=0.1$, p0=30%, p1=50%, 39 HLA A2+ve patients need to be recruited to the study. The drop-out rate is expected to be less than 10% (see section 3.1 for details of patient replacement).

This trial needs to observe a minimum of 16 out of 39 patients who are progression free and alive at 2 years in order to provide evidence that the vaccine warrants further investigation.

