10.2 ANALYSIS PLAN

Molecular Analysis

The analyses on molecular response will be performed on all patients with molecular data at a minimum of 2 post-baseline time points (HLA A2 positive patients must also have received at least 1 dose of the vaccine).

Immunological Analysis

To be evaluable for immunological response, positive HLA A2 patients must receive at least 1 dose of the vaccine and the immunological testing must be available until at least week 8 post first dose.

Safety Analysis

For safety analyses, all patients with positive HLA A2 status who received at least one study drug administration will be evaluable for toxicity. All controls will be included in the safety analyses, where relevant.

Other Analysis

For all other analyses, an intention to treat principle will be used.

10.2.1 ANALYSIS FOR CML PATIENTS ONLY:

Primary:

The primary endpoint is molecular response of BCR-ABL (major or minor response or CMR). For the purpose of analysis, response (as defined by section 9.6) will be measured at weeks 4, 8, 12, 16, 20, 32 and 11, 17 and 23 months. Fisher's exact test will be used to compare differences in proportions of molecular response in CML patients versus controls.

Secondary:

The primary analysis will be repeated for major response or CMR of BCR-ABL.

The analysis methods used for BCR-ABL will be repeated for WT1.

Progression free survival, duration of response and overall survival (as defined in Section 2.2) will be estimated using the method of Kaplan and Meier for each group. Survival estimates will be presented with 90% confidence intervals. These endpoints will also be compared between the CML patients and controls using log-rank tests.

Progression free survival for CML patients is defined in Section 2.2 and is measured as the time from date of consent to the study to date of progression or death from any cause. Alive patients who are progression free will be censored at their date of last follow up. Similar analysis will be performed for overall survival and duration of response.

Toxicity will be collected and evaluated according to the NCI CTC toxicity scale (v4.0) and compared between the vaccinated and control groups by Fisher's exact test.

10.2.2 ANALYSIS FOR AML PATIENTS ONLY:

Primary:

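### Toxicity is compared with controls only within CML and within AML; adding one disease-stratified comparison would use all the data on uncommon vaccine toxicity at little cost

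*Protocol*

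**What the plan says.** The Safety Analysis paragraph of section 10.2 defines the safety population without regard to disease: "all patients with positive HLA A2 status who received at least one study drug administration will be evaluable for toxicity", with all controls included where relevant. It names no test.

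The tests come later. Section 10.2.1, headed for CML patients only, says that toxicity will be graded on the NCI scale and "compared between the vaccinated and control groups by Fisher's exact test". Section 10.2.2, headed for AML patients only, repeats the sentence. Section 10.2.3 covers both diseases but holds only immune endpoints in vaccinated patients.

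The intervention does not differ by disease. Section 1.1.3 states the aim as to "evaluate an identical vaccine strategy in two parallel settings". Sections 5.1 to 5.3 and 6.4.1 give one dose, one schedule, one route and one electroporation procedure. Section 2.2 lists toxicity on CTCAE v4.0 as a secondary endpoint in both diseases.

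The number of controls is left open. Section 3 says, for example, "CML: Control group: all eligible and consenting patients who are HLA A2 negative", and uses the same wording for AML.

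**The concern.** Whether this vaccine, given this way, causes more of some adverse event than is seen in controls is one question, asked in two cohorts of about 32 and 39 vaccinated patients. If the vaccine acts alike in both, two separate tests each see roughly half of the evidence. A moderate excess can then miss significance in both diseases when the two together would show it. The loss is greatest for uncommon events, because Fisher's test on small groups can take only a few p-values. The data for a joint comparison are already being collected: adverse events, blood counts and biochemistry are scheduled in both arms.

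**Working it through.** **Group sizes from the plan.** Section 10.1.1 gives "p0=5%, p1=20%, 32 HLA A2+ve patients need to be recruited to the study" and section 10.1.2 gives "p0=30%, p1=50%, 39 HLA A2+ve patients need to be recruited to the study". Both reproduce with the exact binomial:
- CML, at least 4 of 32: P(X ≥ 4 | 5%) = 0.074 and P(X ≥ 4 | 20%) = 0.907.
- AML, at least 16 of 39: P(X ≥ 16 | 30%) = 0.094 and P(X ≥ 16 | 50%) = 0.900.

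So 32 and 39 are sound sizes for the vaccinated groups. The protocol states no power for toxicity.

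**Assumptions.** One control per vaccinated patient (32 and 39), a two-sided 5% level, and event rates chosen to span uncommon to common. None of these stands in the protocol, so each is varied below.

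**Method.** For each disease, power is the sum of the product of the two binomial probabilities over all tables where Fisher's p ≤ 0.05. The chance that at least one of two independent tests rejects is 1 − (1 − a)(1 − b). The stratified test is the exact conditional test, using the convolution of the two hypergeometric distributions.

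**Why small groups matter.** With no control events in CML, 5 v 0 gives p = 2 × C(32,5)/C(64,5) = 2 × 201,376/7,624,512 = 0.053, which is not significant. Six events are needed, and at a 10% rate 3.2 are expected. Across both diseases, six events split 3 and 3 against none give p = 2 × (4,960/41,664) × (9,139/76,076) = 0.029, and 7.1 events are expected.

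**Main results (1:1, two-sided 5%).**

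| Control v vaccinated | CML | AML | Either | Stratified |
|---|---|---|---|---|
| 1% v 10% | 7.1% | 13.9% | 20.0% | 52.6% |
| 5% v 20% | 27.6% | 39.5% | 56.2% | 73.0% |
| 5% v 30% | 68.0% | 80.7% | 93.8% | 98.0% |

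For the first row, either = 1 − 0.929 × 0.861 = 0.200.

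**Sensitivity (CML / AML / either / stratified).**
- 1% v 10%, 0.5 controls per vaccinated patient: 1 / 3 / 4 / 24%.
- 1% v 10%, 1.25 controls: 29 / 40 / 58 / 73%.
- 1% v 10%, 2 controls: 49 / 60 / 80 / 86%.
- 1:1, 0.5% v 5%: 0.4 / 1.0 / 1.4 / 11%.
- 1:1, 2% v 20%: 46 / 62 / 80 / 94%.
- 1% v 10%, 1:1, one-sided 5%: 16 / 26 / 38 / 67.5%.
- 1% v 10%, 1:1, 36 CML patients (the recruitment figure in 10.1.1): 11 / 14 / 23 / 57%.

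**False positives.** With no vaccine effect and a background of 5, 10 or 15% in both arms, the stratified test rejects in 1.4, 2.6 and 2.9% of trials. The gain does not come from a looser test.

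**Precision.** With common rates and a common control ratio, interval width scales with 1/√n. The stratified risk difference would have an interval about 1 − √(32/71) = 33% narrower than CML alone and 1 − √(39/71) = 26% narrower than AML alone.

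**Excess in AML only (1:1; AML Fisher against stratified).**
- 10% in all other groups, 30% in vaccinated AML: 52% against 36%.
- 10% and 40%: 84% against 68%.
- 20% and 50%: 73% against 53%.

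**The case against.** The case for leaving the plan alone is substantial. The trial is two separately sized cohorts with their own endpoints and controls, so analysing a secondary endpoint within each follows from the design. The two settings also differ clinically: AML patients enter after chemotherapy, possibly with incomplete count recovery, while CML patients stay on a tyrosine kinase inhibitor. Section 7.1.8 foresees cytopenia in patients with low marrow reserve, which could concentrate an excess in one disease. There the stratified test loses power. This stands, and it is why the per-disease tests should not be replaced or demoted.

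A reader might infer that separate testing is an error, or that it contradicts section 10.2. It does neither. That paragraph says who is evaluable and names no test. A stratified summary could also be in the statistical analysis plan, which is not at hand.

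A reader might take 7 to 14% against about 53% as the general cost for any tenfold rise. Those figures need a 1% control rate, exactly equal arms and a two-sided 5% level. Equal arms are an unfavourable point for Fisher's test. The fairer contrast is with the chance that either test rejects, 20% in that scenario.

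A reader might also infer that the trial would declare the vaccine safe because these tests were not significant. No rule in the protocol uses them so. Safety oversight runs through the discontinuation criteria (4.4, 4.5) and review by the TMG and DMEC (12.1).

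Finally, any comparison with controls is limited. Controls skip visits 2 and 5 and have no scheduled ECG, CK or post-baseline autoimmune profile. The added comparison must be restricted accordingly.

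**Conclusion.** The point holds as an optional improvement. The protocol's only vaccinated-against-control toxicity tests are within disease, while the intervention and toxicity scale are common to both, so evidence on uncommon vaccine toxicity is not fully used. With 1:1 controls and a two-sided 5% level, the stratified test gains about 33 percentage points over the chance that either separate test rejects at 1% v 10% (53% against 20%), about 17 points at 5% v 20% (73% against 56%), and about 4 points at 5% v 30% (98% against 94%). The direction was the same at every control ratio and base rate tried, provided the vaccine effect is the same in both diseases. The size depends on control numbers, event rates and a significance level that the protocol does not give. If the excess is in one disease only, the per-disease test does better.

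**What to change.** In section 10.2, Safety Analysis, add one comparison of all dosed HLA A2-positive patients against all controls, stratified by disease (exact Cochran-Mantel-Haenszel). Limit it to event types ascertained at visits common to both arms. Report a stratified risk difference with its confidence interval, and state the significance level and sidedness. Keep the Fisher tests of 10.2.1 and 10.2.2 alongside with the same standing.

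The cost is one paragraph and a little programming, with no new data. The downside is one more test, which assumes a similar vaccine effect in both diseases; the per-disease results show whether that is reasonable.

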Title:	WT1 Immunity via DNA fusion Gene Vaccination in Haematological Malignancies by intramuscular injection followed by intramuscular electroporation.
Sponsor:	University Hospital Southampton NHS Foundation Trust
Sponsor Ref Number:	RHMCAN0700
Funder:	Leukaemia & Lymphoma Research, and the Efficacy and Mechanism Evaluation (EME) programme.
Trial Phase:	II
Indication:	Chronic Myeloid Leukaemia (CML) and Acute Myeloid Leukaemia (AML)
Primary Objective:	CML: Molecular response of BCR-ABL. AML: Time to disease progression.
Secondary Objective:	Molecular response of WT1 transcript levels, immune responses to WT1 and DOM, Toxicity, CML-Time to disease progression, next treatment and survival, AML-2 year survival, overall survival
Trial Design:	Open label, single dose level, Phase II study in two patient groups (CML and AML) using genetic randomisation. Consented and eligible HLA A2+ve patients will be vaccinated with two DNA vaccines. HLA A2 –ve patients will be followed up on trial without vaccination.
Sample size : (split by treatment group)	Vaccination Arm (HLA A2+ve patients): 32 patients with data to at least 8 weeks will be recruited into the CML treatment group. 39 patients with data to at least 8 weeks will be recruited into the AML treatment group. Control Arm: this arm will consist of all eligible and consenting patients who are HLA A2 –ve.
Main inclusion Criteria:	CML: Philadelphia chromosome positive CML in chronic phase, in complete cytogenetic response (CCyR) but with detectable BCR-ABL transcripts and maintained the CCyR on tyrosine kinase inhibitor (TKI) monotherapy for a minimum of 24 months. AML: WT1 ⁺ AML in CR or morphologic CR with incomplete blood count recovery (CRi).
Main exclusion Criteria:	CML: accelerated phase or blast crisis or having achieved CMR at any point during tyrosine kinase inhibitor therapy. Tyrosine kinase inhibitor dose modification in the previous year or interruption for > 15 days in the previous 6 months prior to recruitment.
Investigational Products:	p.DOM-WT1-37 DNA Vaccine p.DOM-WT1-126 DNA Vaccine

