4.2 EXCLUSION CRITERIA

CML patients:

- CML in accelerated phase or blast crisis or having achieved CMR at any point during tyrosine kinase inhibitor therapy
- Tyrosine kinase inhibitor change or dose modification in the previous year, therapy interruption for more than 15 days in the previous 6 months to enrolment
- Prior interferon-α therapy
- Hypocellular bone marrow (<20%) (indicated by blood counts and most recent bone marrow (where available)
- Complete molecular response (CMR)

AML patients:

- AML in haematological relapse or eligible for allogeneic SCT.
- Hypocellular bone marrow (<20%)
- AML patients with the "good-risk" abnormalities comprised by the core binding factor leukaemias (i.e., AML with the translocation (8;21) and inversion of chromosome 16, and acute promyelocytic

leukaemia with the translocation (15;17))

All patients:

- Systemic steroids or other drugs with a likely effect on immune competence are forbidden during the trial. The predictable need of their use will preclude the patient from trial entry. Inhaled steroids are allowed.
- Major surgery in the preceding three to four weeks from which the patient has not yet recovered.
- Patients who are of high medical risk because of non-malignant systemic disease, as well as those with active uncontrolled infection.
- Patients with any other condition which in the Investigator's opinion would not make the patient a good candidate for the clinical trial, such as concurrent congestive heart failure or prior history of New York Heart Association (NYHA) class III/ IV cardiac disease
- Current malignancies at other sites, with the exception of adequately treated basal or squamous cell carcinoma of the skin. Cancer survivors, who have undergone potentially curative therapy for a prior malignancy, have no evidence of that disease for five years and are deemed at low risk for recurrence, are eligible for the study.
- Patients who are serologically positive for or are known to suffer from Hepatitis B, C, Syphilis or HIV. Counselling will be offered to all patients prior to testing.

4.3 **REGISTRATION PROCEDURE**

All registration and baseline assessments should be completed prior to registration.

Only patients fulfilling the eligibility criteria should be registered, any queries should be discussed with the University of Southampton Clinical Trials Unit before registration

All patients must be registered via the University of Southampton Clinical Trials Unit on:

[contact]

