The primary endpoint is time to disease progression measured as the time from date of consent to the study to date of progression or death from any cause (progression is defined as disease relapse). Alive patients who are progression free will be censored at their date of last follow up. Progression free survival will be estimated using the method of Kaplan and Meier for each group. Survival estimates will be presented with 90% confidence intervals. A log rank test will be computed to compare AML patients and their controls.

Secondary:

The primary analysis will be repeated for survival time.

A secondary endpoint is molecular response of WT1 (major or minor response or CMR). For the purpose of analysis, response (as defined in section 9.6) will be measured at weeks 4, 8, 12, 16, 20, 32 and 11, 17 and 23 months. Proportions of responders in the vaccinated group will be compared with the control group using Fisher's exact test for the CML and AML groups. This analysis will be repeated for major molecular response or CMR of WT1.

Toxicity will be collected and evaluated according to the NCI CTC toxicity scale (v4.0) and compared between the vaccinated and control groups by Fisher's exact test.

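### The primary AML comparison with HLA A2 negative controls is a log-rank test with no strata or covariates in a non-randomised study, so any imbalance in cytogenetic risk passes into the result

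*Protocol*

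**What the plan says.** Section 10.2.2 defines the AML primary endpoint: "The primary endpoint is time to disease progression measured as the time from date of consent to the study to date of progression or death". Deaths of every cause count as events. Its only between-arm test follows: "A log rank test will be computed to compare AML patients and their controls". The primary analysis is then repeated for survival time, so overall survival inherits the same test.

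On allocation, section 3 reads "This is a non-randomised open label, single dose level Phase II study in two patient groups (CML and AML) based on HLA A2 genotype", while the synopsis speaks of a "Phase II study in two patient groups (CML and AML) using genetic randomisation". The comparator has no fixed number and no balancing: "AML: Control group: all eligible and consenting patients who are HLA A2 negative".

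On prognosis, the Figure 1 caption in section 1.1.3 says that overall survival and "relapse risk (B) in MRC AML11 trial are shown by hierarchical risk group", with favourable, intermediate and adverse groups. Section 4.2 excludes the good-risk "abnormalities comprised by the core binding factor leukaemias" and acute promyelocytic leukaemia, which leaves the intermediate and adverse groups. The baseline marrow for AML patients includes cytogenetics in both observation schedules, and demographic data are collected in both arms. CR or CRi is an entry criterion (section 4.1).

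**The concern.** With arms set by genotype and a control group that is simply whoever is eligible, HLA A2 negative and consenting, nothing in the design balances cytogenetic risk. An unstratified log-rank test attributes any resulting difference in relapse to the vaccine. With about 39 vaccinated patients, a moderate difference in the share of adverse-risk disease could create an apparent benefit or hide a real one. If adjustment is introduced only after an imbalance has been seen, it is post hoc and carries less weight. A second, smaller matter is that ignoring a prognostic factor can cost power.

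**Working it through.** **1. The plan's own figure.** Section 10.1.2 gives p0 = 30%, p1 = 50%, α = β = 0.10, n = 39, and success at 16 or more progression free and alive at 2 years. Exact binomial: P(X ≥ 16 | 39, 0.30) = 0.0944 and P(X ≥ 16 | 39, 0.50) = 0.9002. The smallest n meeting both limits is 39, with 16 as its only cut-off. The design reproduces. It is single-arm, and no power is stated for the log-rank test.

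**2. What the log-rank test can do as it stands.** With exponential times the implied hazard ratio is ln(0.5)/ln(0.3) = 0.576. The control number is open; take 39. Events by 2 years: 39 × 0.7 + 39 × 0.5 = 46.8. Schoenfeld power at two-sided 0.05 is Φ(√(46.8 × 0.25) × |ln 0.576| − 1.96) = Φ(1.89 − 1.96), about 47%. With 60 controls it is 56%. At two-sided 0.10 the figures are 60% and 68%.

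**3. Assumed inputs.** The protocol gives neither the adverse versus intermediate hazard ratio h nor the adverse share. Assumed: h from 1.5 to 3 and share 15% to 50%. The lower end has a loose link to the text. If the 60–75% two-year relapse range in section 1.1.3 is read as the two risk groups, which is an inference, h = ln(0.25)/ln(0.40) = 1.51.

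**4. How often chance produces an imbalance.** With 39 per arm and a true adverse share of 30% in both, the observed shares differ by 10 points or more, in either direction, in about 39% of trials, and by 20 points or more in about 6%.

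**5. Effect of an imbalance with no vaccine effect.** Suppose 20% adverse among vaccinated patients and 40% among controls. Set x, the 2-year PFS of intermediate-risk patients, so that a 30% adverse mix has 2-year PFS of 30%: 0.7x + 0.3x^h = 0.30. For h = 2, x = 0.370. Then:
- vaccinated: 0.8 × 0.370 + 0.2 × 0.137 = 0.323
- controls: 0.6 × 0.370 + 0.4 × 0.137 = 0.277
- crude hazard ratio, approximately: ln(0.323)/ln(0.277) = 0.88

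The test results come from simulation with exponential times, censoring at 36 months and 39 per arm:

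| h | Crude HR | False benefit, unstratified (nominal 2.5%) | False benefit, stratified |
|---|---|---|---|
| 1.51 | 0.92 | about 5% | 2.5–3% |
| 2 | 0.88 | about 7–7.5% | 2.5–3% |
| 3 | 0.83 | about 10–12% | 2.5–3% |

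The ranges cover two separate sets of runs.

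**6. Balanced on average.** With no vaccine effect and an equal expected risk mix (30% adverse, h = 2 or 3), false benefit is 2.8% unstratified and 2.1–3.0% stratified. Over repeated trials the unstratified test holds its error; the excess in step 5 is conditional on an imbalance.

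**7. Power.** Two-year PFS 30% versus 50%, two-sided 0.05, 39 per arm: unstratified power is about 54–56%. Over 39 or 60 controls, stratifying adds about 0–1 point at h = 1.5, about 1–4 at h = 2 and about 4–11 at h = 3.

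**The case against.** **Strata and covariates usually belong in the SAP, which is not at hand.** This is partly right: their absence alone would be no finding. But the protocol does fix the primary between-arm test, and without a change of wording an adjusted analysis added in a SAP would rank behind it. What is criticised is the choice that is stated.

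**The decision rule is single-arm.** This stands. A reader might infer that the go/no-go decision is compromised. Section 10.1.2 rests it on 16 of 39 vaccinated patients, and no change to the log-rank test alters that.

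**The unstratified test loses power.** A reader might infer a material loss. The documents do not support it: the loss depends on a hazard ratio they do not give, and the only value loosely linked to their figures, 1.51, makes it about a point at most. The larger power problem is that the log-rank test was never sized (step 2), and stratifying does not cure that.

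**Genotype allocation behaves like randomisation.** Nothing in the protocol links HLA A2 to cytogenetic risk, and section 9.1 lists HLA typing among tests done after consent and registration, which limits selection by arm. So a reader should not infer that systematic confounding has been shown. It is possible: chest X-ray, ECG and echocardiogram at entry are for HLA A2 positive patients only, while cardiac disease is a ground for exclusion. Cytogenetic strata would not remove a difference of that kind.

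**The size of the bias rests on the same unknown hazard ratio.** This also stands. The Figure 1 curves cannot be read in the text at hand, and the favourable group is excluded, so the remaining contrast is not quantified. That is why a range is shown.

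**Conclusion.** The point holds as a matter of protection against bias. The primary AML comparison is unadjusted in a non-randomised study, and an imbalance in a factor by which the protocol itself presents relapse would pass into the result. Under an assumed 20% versus 40% adverse-risk split and prognostic hazard ratios of 1.5 to 3, false benefit at a nominal 2.5% becomes about 5% to 12%, against about 2.5% with stratification. A chance gap that large, in either direction, is uncommon (about 6% of trials at a 30% share); gaps of 10 points or more are frequent (about 39%). These figures assume 39 controls, exponential times and inputs that the protocol does not state. The power gain is secondary and may be negligible. The change is worth making because it is cheap and must be fixed in advance to carry weight.

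**What to change.** In section 10.2.2, make the between-arm comparison a log-rank test stratified by cytogenetic risk at diagnosis (intermediate versus adverse), with a pre-set rule for failed or missing karyotype. Report a Cox hazard ratio with a 90% confidence interval, in line with the level already used there, stratified by risk and adjusted for age and, if event numbers allow, for CR versus CRi. With 39 per arm, about 47 events are expected by 2 years, so the covariate list should stay short. Keep the unstratified log-rank test as supportive, and apply the same scheme to overall survival.

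The cost is more than wording. Eligibility requires only that the good-risk lesions be absent, and the scheduled marrow is taken in remission, where the diagnostic karyotype may not show. The diagnostic risk class therefore has to be recorded for every AML entrant from the malignancy history. A few patients may be misclassified, especially those placed by the missing-karyotype rule.
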